### **3.1.3 Trial Schedule**

The first subject is expected to be enrolled in Q4 2016 and the last follow-up visit is expected to take place in Q1 2018. The duration of the trial is expected to be approximately 1-1.5 years. The end of trial is defined as the follow-up visit for the last subject.

### **3.2 Planned Number of Trial Sites and Subjects**

The trial will be conducted at one site, University of Barcelona, Hospital clinic, Spain, including patients with cirrhotic portal hypertension, 6 patients in Part 1 completing all Visit 2-assessments, and approx. 20 patients in Part 2, at least 18 of which in Part 2 with HVPG  $\geq$  12 mmHg at baseline.

### **3.3 Interim Analysis**

No formal statistical interim analysis is planned.

### **3.4 Safety Review Committee (SRC)**

An SRC, comprising at least one external expert in addition to the Principal Investigator and the Ferring representatives, will evaluate the safety, tolerability and pharmacodynamics of the compound.

Two scheduled meetings are planned: One SRC meeting will be held after the first 3 patients in Part 1 have completed all Visit 2 assessments, where the SRC will recommend whether the doses can be increased as planned or if a modified (lower) dose regimen should be applied. Another SRC meeting will be held after all subjects in Part 1 have completed all Visit 2 assessments in order to determine the dose that will be used in Part 2 of the trial. Furthermore, unscheduled meetings can be demanded anytime for any reasonable cause by the sponsor or the Investigator, e.g. due to any unforeseen adverse events. In such a situation, the SRC will recommend whether the dosing should continue according to the pre-defined dosing schedule, be changed to a different dosing schedule, or whether dosing should be stopped. A working procedure for the SRC will be described prior to study initiation.

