It is essential that FE 204205 is administered intravenously, since other routes of administration may cause degradation of the molecule resulting in the generation of the full agonist M1, as shown following subcutaneous administration in healthy subjects. Adequate procedures are in place, according to standard medical practice, to avoid extravasation, i.e. accidental injection or leakage of FE 204205 into the subcutaneous space or perivascular tissues.

The above mentioned risks are addressed in the inclusion and exclusion criteria for the trial and will be closely monitored through safety laboratory evaluations, cardiovascular monitoring including vital signs and ECG, AE reporting, and by safety review committee (SRC) evaluations. The risk posed to the patients participating in the trial is deemed low and ethically justifiable. For more detailed information on FE 204205 please refer to the Investigator's Brochure (6).

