### **3.5.3 Blinding**

Since all subjects in Part 1 receive the same treatment, Part 1 is open-labelled.

Part 2 of the trial is double-blind, keeping all subjects and personnel involved in the trial blinded to the treatment received. Blinding is performed to reduce any bias concerning reporting and interpretation of e.g. AEs. If unblinding is deemed appropriate, the blinding for a patient need not be kept once the patient have been treated and all data are entered in the eCRF.

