The chosen dose increments between dose levels (increasing by a factor of 2.5 from the starting dose, then maximum increase of factor 2 for the subsequent doses) are lower and thus more conservative than the ones used in the trials with healthy subjects, where a factor of  $\sim 3$  was applied for the respective dose range from 0.005 mg/hr to 0.05 mg/hr.

In Part 2 each patient will receive a 2-hour intravenous infusion of the dose of FE 204205 selected by the SRC, or placebo, on Day 1. The SRC will select the dose based on incidence and frequency of adverse events, safety laboratory data, ECG, systemic and portal haemodynamic parameters. The dose selected will be the maximum tolerated dose (MTD) or a lower dose. The MTD is defined as the dose level below the dose where one or more stopping criteria, as confirmed by a second measurement, are met in at least two subjects in Part 1.

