#### **4.5 Stopping Criteria**

The infusion will be interrupted and may be adjusted in the subject if any of the below stopping criteria occur, and halted for evaluation by the SRC when one or more criteria, as confirmed by a second measurement, are met in at least two subjects receiving the same treatment.

- Systolic blood pressure increased by 50% or more from the baseline and reaching >160 mmHg
- Systolic blood pressure 180 mmHg or higher
- Diastolic blood pressure 105 mmHg or higher
- Mean arterial pressure 130 mmHg or higher
- Heart rate 45 beats per minute or lower
- Signs or symptoms of mesenteric or peripheral ischemia, or hypertensive crises.

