### 8.3 Adverse Events of Special Interest

Taking into account the pharmacological profile of FE 204205, AEs related to exaggerated pharmacological effects, e.g. peripheral ischemia, increased blood pressure, and decreased cardiac output will be closely monitored.

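### In Part 1, a single case of mesenteric or peripheral ischaemia or hypertensive crisis does not require Safety Review Committee review before the next patient is dosed

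*Combined protocol and SAP*

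**What the plan says.** Section 3.4 fixes two SRC meetings: one after the first three Part 1 patients have completed Visit 2, and one after all Part 1 subjects have. Beyond these, "unscheduled meetings can be demanded anytime for any reasonable cause by the sponsor or the Investigator, e.g. due to any unforeseen adverse events". Section 5.1.1.1 likewise leaves unscheduled meetings to the judgement of the investigator or the sponsor.

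Section 4.5 sets the response to a stopping criterion in one subject: "The infusion will be interrupted and may be adjusted in the subject if any of the below stopping criteria occur". Dosing is halted for SRC evaluation only when one or more criteria, as "confirmed by a second measurement, are met in at least two subjects receiving the same treatment". The list contains five blood pressure and heart rate limits and one clinical item, "Signs or symptoms of mesenteric or peripheral ischemia, or hypertensive crises". The clinical item has no rule of its own. The definition of the maximum tolerated dose in 3.5.4 uses the same count: criteria that "are met in at least two subjects in Part 1".

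Section 4.4 obliges the investigator to withdraw a subject who shows signs of a serious treatment-emergent event, and 4.6 has withdrawn Part 1 subjects replaced. Neither mentions the SRC. Section 8.3 says that "AEs related to exaggerated pharmacological effects, e.g. peripheral ischemia, increased blood pressure, and decreased cardiac output will be closely monitored" and attaches no further action. Section 3.1.2 doses patients one at a time, with a minimum of 3 days between successive first doses.

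**The concern.** This is the first study of the drug in patients with cirrhotic portal hypertension, and the class hazard named in Section 1.1 is excessive vasoconstriction leading to tissue hypoxia and ischaemia. Among the controls on the trial's risks, Section 1.3 counts "cardiovascular monitoring including vital signs and ECG, AE reporting, and by safety review committee (SRC) evaluations". In the text available, the external expert's only described role is as a member of the SRC.

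A rule needing a repeat measurement and a second subject suits a blood pressure reading, which can be transient or an artefact. It suits clinical ischaemia poorly: one case is already the harm the trial is meant to detect. Under the text as it stands, whether the external expert sees that case before another patient is exposed depends on a decision by the sponsor or the investigator.

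**Working it through.** The plan gives no figure for this rule, so there is none to reproduce. The check compares the sections and then counts days and patients.

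**1. Can one case trigger mandatory review?** The phrase about the same treatment in 4.5 has two readings.

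- All of Part 1, which 3.5.3 supports: "Since all subjects in Part 1 receive the same treatment, Part 1 is open-labelled". The trigger is then two of six planned patients.
- One dose level. Table 5-1 plans only three patients at 0.1 mg, so the trigger there is two of three.

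One case is insufficient on either reading.

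**2. Does another section fill the gap?** Withdrawal (4.4), replacement (4.6), special-interest monitoring (8.3) and the stagger (3.1.2) contain no SRC step. Section 8.5.2 brings a serious adverse event (AE) to the sponsor within 24 hours, after which calling the SRC is optional under 3.4.

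**3. Days available.** Inputs: 3 days between first doses (3.1.2) and the planned doses in Table 5-1. Take an event on Day d of the index patient.

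- Earliest first dose in the next patient = index Day 1 + 3 = Day 4, so the gap is 4 − d.
- The next patient's own Day d falls on index Day d + 3, so the planned event dose is reached (d + 3) − d = 3 days after the event.

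| Event day | Planned dose, patients 1–3 / 4–6 (mg) | Days to next first dose | That first dose (mg) | Days to event dose | Escalations needed |
|---|---|---|---|---|---|
| 1 | 0.01 / 0.025 | 3 | 0.01 / 0.025 | 3 | 0 |
| 2 | 0.025 / 0.05 | 2 | 0.01 / 0.025 | 3 | 1 |
| 3 | 0.05 / 0.1 | 1 | 0.01 / 0.025 | 3 | 2 |

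After a Day 3 event the next patient therefore starts at one fifth (0.01/0.05) or one quarter (0.025/0.1) of the event dose. The 3-day figure assumes that both patients are in the same block and that the index patient escalated as planned. If the index patient had repeated a dose (say 0.01, 0.01, 0.025 mg, with the event on Day 3), the next patient's planned 0.025 mg falls on index Day 5, which is 2 days after the event.

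**4. Patients dosed before the next scheduled meeting.** Each scheduled meeting follows three completers. For an event in the kth patient of a block (k = 1, 2, 3):

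- index patient completes Visit 2: 3 − k = 2, 1, 0 further patients;
- index patient is withdrawn and replaced: at least 4 − k = 3, 2, 1.

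The second line is the more likely one for a serious event, given 4.4. Both counts apply unless the SRC is called, the trial is stopped, or a second subject triggers 4.5.

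**5. Scale, illustration only.** The documents give no event rate. Assume independent events with per-patient probability p, and three patients at a dose.

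- Exactly one case, so no mandatory review: 3p(1 − p)² = 3 × 0.1 × 0.81 = 0.243 at p = 0.1, and 3 × 0.3 × 0.49 = 0.441 at p = 0.3.
- Two or more, so the rule fires: 3p²(1 − p) + p³ = 0.027 + 0.001 = 0.028 at p = 0.1, and 0.189 + 0.027 = 0.216 at p = 0.3.

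Over this assumed range, a lone case is more likely than the pair that compels review.

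**The case against.** The best defence is that the substance is already provided. Section 3.4 allows a meeting at any time, gives unforeseen adverse events as its example, and lets the SRC recommend continuing, changing or stopping. The investigator and the sponsor sit on the SRC, and either can stop the trial (4.4). The infusion is interrupted at the first criterion, patients are dosed singly, escalation has its own limits, and the SRC must meet before the regimen rises to 0.1 mg. All of this stands, and it limits the size of the point. It makes review possible after one case; it does not make it compulsory.

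A second defence is unseen text. Section 3.4 promises an SRC working procedure, which may well contain event triggers, and parts of 1.3 and 3.5.4 were not in the text reviewed. This also stands, and the conclusion is confined to the text available.

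Three stronger readings are tempting and should not be drawn.

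- A reader of 4.5 alone might infer that a patient with ischaemia need not be withdrawn. Sections 4.4 and 3.5.7 call for withdrawal when the event is serious, as these events plausibly would be.
- A reader might take the 1-day gap after a Day 3 event as the time to re-exposure at the same dose. On the planned schedule it is the time to the block's lowest dose.
- A reader might want every drug-related withdrawal to trigger the SRC. That would include non-serious withdrawals for expected pharmacological effects and would partly undo the two-subject blood pressure and heart rate rule, which is a reasonable choice.

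**Conclusion.** The point holds in a limited form. As written, the plan lets the next Part 1 patient be dosed after one case of ischaemia or hypertensive crisis without SRC review, because the mandatory trigger needs two subjects and every other route is discretionary. This follows from a stated rule and is not simply a missing detail.

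The size is modest. The first dose that could precede review is the block's lowest, and at least three further patients could be dosed before the next scheduled meeting in the worst position (first in a block, withdrawn and replaced). The day counts rest on the minimum stagger and the doses in Table 5-1; the patient counts rest on the plain reading that scheduled meetings wait for three completers. No event probability is claimed. The documents do not support calling the design unsafe or invalid, since individual protections and discretionary powers are in place. Confidence is medium because the working procedure could not be checked.

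**What to change.** Leave the two scheduled meetings as they are, and keep the two-subject rule for the blood pressure and heart rate criteria. Add to 4.5, with a cross-reference in 3.4:

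> In Part 1, if any one patient shows signs or symptoms of mesenteric or peripheral ischaemia or hypertensive crisis, or has a serious AE with a reasonable possibility of being caused by the IMP, no further patient will receive a first dose until the SRC has reviewed the case and recommended whether dosing continues, is changed or stops.

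The serious-AE clause covers the route through 4.4 and 4.6, where a withdrawn patient is replaced without review. Non-serious drug-related withdrawals are deliberately left out. If the SRC working procedure already contains this rule, citing it in 3.4 is enough.

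The cost is one ad hoc SRC contact and possibly some days' delay per event. The trigger uses information already collected: the 4.5 list, seriousness and causality. Part 1 is open-label, so no blinding problem arises. Screening opens on Day -21, which often leaves room for a short call, but a patient screened near that limit might need rescreening, given the 5-week cap per subject in Section 6.

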### **3.5 Discussion of Overall Trial Design and Choice of Control Groups**

#### **3.5.1 Trial Design**

The purpose of Part 1 is to assess safety, tolerability, and pharmacodynamics in the dose interval 0.01-0.1 mg i.v. infusion over 2 hours, and thus determine the maximum tolerated dose within this dose interval. Part 1 is open-label since it comprises only one treatment arm, and it was neither regarded necessary nor ethically justifiable to include placebo treatment. The assessment of systemic and portal hemodynamics by pulmonary artery and hepatic vein catheterization on Day 3 will enable a more precise evaluation of the hemodynamic effect at the maximum tolerated dose, compared to non-invasive vital signs assessments.

Part 2 is aiming at defining the anticipated maximal effects of a single intravenous dose of FE 204205 on portal haemodynamics. Part 2 of the trial is randomised and placebo-controlled in order to correct for the non-treatment related factors that otherwise may have an impact on the evaluation of FE 204205. All subjects will be randomly allocated to active treatment or placebo in a double-blind setting, i.e. the active or placebo treatment will not be revealed to the subjects or the personnel involved in the trial. The randomisation is standard procedure in studies with more than one treatment arm.

### **3.5.2 Selection of Endpoints**

Since this is the first study with FE 204205 in patients with cirrhotic portal hypertension the selected endpoints focus on the evaluation of safety and tolerability of the treatment in general, the pharmacokinetics of FE 204205, and investigation of the pharmacological activity including the pharmacodynamic response.

HVPG is the golden standard for evaluation of portal hypertension in patients with cirrhosis. Measurements of HVPG is a safe procedure and it is used routinely in clinical practice in patients with chronic liver disease. The methodology and consistency of the HVPG measurements are crucial in the evaluation of treatment effects. This is ensured by all measurements being performed at one site with the same personnel.

### **3.5.3 Blinding**

Since all subjects in Part 1 receive the same treatment, Part 1 is open-labelled.

Part 2 of the trial is double-blind, keeping all subjects and personnel involved in the trial blinded to the treatment received. Blinding is performed to reduce any bias concerning reporting and interpretation of e.g. AEs. If unblinding is deemed appropriate, the blinding for a patient need not be kept once the patient have been treated and all data are entered in the eCRF.

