## 5.5 Blinding / Unblinding

### 5.5.1 Blinding

Part 1 of the trial is open-labelled. In Part 2, all subjects, the Investigator, and all staff involved in the conduct of the trial will be blinded to the treatment received. The trial monitor will not be blinded, and no specific precautions will be taken to keep the pharmacist or personnel running the analyses of FE 204205 blinded.

It is the responsibility of the pharmacy to ensure that the syringes used for infusion in Part 2 are identical and non-distinguishable.

The pharmacy will receive the computer-generated randomisation list from Global Biometrics, Ferring Pharmaceuticals A/S.

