### 5.5.2 Unblinding of Individual Subject Treatment

An emergency decoding system will be available to the Investigator at University of Barcelona Hospital Clinic and to designated persons at Ferring Pharmaceuticals for each subject. Breaking of the blind for individual subjects in emergency situations is only permitted in case of a serious, unexpected, or other important AE, when the knowledge of the trial medication in question is required for therapeutic decisions and for the management of the subject. As far as the emergency permits, the need to break the blind will be agreed by the Investigator and Ferring. If the blinding is broken it must be documented by whom, reason and the date of unblinding.

If it is necessary to unblind an individual subject's treatment for the purposes of expedited reporting to the authorities and/or IEC, only those individuals within Ferring whose responsibility it is to report this information will know the identity of the trial medication. Every attempt will be made to try to keep all other trial and site personnel blinded throughout the course of the trial.

Information on whether the blind has been broken for any subjects must be collected before the database is declared clean and is released to the statistician.

If unblinding is deemed appropriate, the blinding for a patient need not be kept once the patient have been treated and all data are entered in the eCRF.

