### **9.3 Protocol Deviations**

The rating of protocol deviations will be decided on the basis of a review of the data before unblinding of the data and the declaration of 'clean file' and database lock. Major protocol deviation criteria will be specified in the statistical analysis plan.

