#### **9.4.2 Per Protocol Analysis Set**

The per protocol (PP) analysis set comprises all dosed patients with no major protocol deviations and with HVPG $\geq$ 12 mmHg at baseline. For subjects encountering a major protocol deviation after study treatment has been initiated, data after the point at which the first deviation occurs will be excluded from all evaluations. Final decisions for exclusion of subjects/subject data from the PP analysis set will be made when a clean database is available to review ahead of database lock. The PP analysis set will be used for the PK analysis with the exception that specific subjects may be excluded if certain PK parameters cannot be estimated with sufficient precision (criteria for which will be further detailed in the Statistical Analysis Plan)

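### A Part 2 patient's blind may be dropped at discretion once data are entered, before deviation review, per-protocol decisions or database lock

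*Combined protocol and SAP*

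**What the plan says.** Section 3.5.3 (Blinding) describes Part 2 as double-blind and gives the purpose: to reduce bias in reporting and interpreting, for example, adverse events. The same paragraph then adds: "If unblinding is deemed appropriate, the blinding for a patient need not be kept once the patient have been treated and all data are entered" (entry meaning into the eCRF). Section 5.5.2 (Unblinding of Individual Subject Treatment) repeats it as a paragraph of its own: "If unblinding is deemed appropriate, the blinding for a patient need not be kept once the patient have been treated", with the same data-entry condition.

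The general statements are these:

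- Section 3.5.1: "the active or placebo treatment will not be revealed to the subjects or the personnel involved in the trial".
- Section 5.5.1: "all subjects, the Investigator, and all staff involved in the conduct of the trial will be blinded to the treatment received". That section exempts the monitor, and takes no precautions to keep the pharmacist or the bioanalysts blinded. These exemptions are by role, not by time.

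The other routes in section 5.5.2 have limits. Emergency code-breaking is for important adverse events where management of the subject requires the treatment to be known. Unblinding for expedited reporting is confined to the sponsor staff who must report, and "Every attempt will be made to try to keep all other trial and site personnel blinded throughout the course of the trial". Section 5.5.2 also requires that a broken blind be documented, and "Information on whether the blind has been broken for any subjects must be collected before the database is declared clean".

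On later decisions, section 9.3 says the rating of deviations "will be decided on the basis of a review of the data before unblinding of the data". Section 9.4.2 says: "Final decisions for exclusion of subjects/subject data from the PP analysis set will be made when a clean database is available to review".

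**The concern.** The clause is a stated permission, not a missing detail. It operates patient by patient, while the trial may still be recruiting, and it has no owner and no list of recipients. Three features of the trial make that matter:

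- All HVPG measurements are made at one site by the same personnel (section 3.5.2), who go on to measure later patients.
- Adverse drug reactions are defined by the investigator's causality judgement (section 9.6.2.4).
- The per-protocol set depends on a deviation review and on exclusion decisions that have not been made when the clause becomes available (sections 9.3 and 9.4.2).

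At stake is the protection that section 3.5.3 says blinding is there to give. The unblinded patient's own HVPG values and causality assessments are already entered, so the exposure lies in decisions still to be made about that patient and in the assessment of later patients.

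**Working it through.** **Text check.** The clause sets two conditions: the patient has been treated, and all data are in the eCRF. Since the sentence concerns the blinding of one patient, the natural reading is that patient's data, although it does not say so outright. Neither section ties the permission to the end of Part 2. Sections 3.5.1 and 5.5.1 do not refer to it.

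**Route 1: decisions about the unblinded patient.** Deviation rating and per-protocol decisions come at data review, after entry. Between the two, the clause lets the treatment be known. No number applies.

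**Route 2: inference about later patients.** The plan gives no figure here, so this is an illustration.

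Inputs:

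- 16 active and 4 placebo, total 20 (section 9.1). 16/4 = 4, which agrees with the stated 4:1 ratio. The synopsis says approximately 20; exactly 16:4 is assumed.
- Block size is not stated (section 4.2.2). Two cases are shown: unblocked, and blocks of five known to the site.
- Follow-up is 4 to 11 days after dosing (section 6.2, Visit 3).
- Assumed: the clause is used during enrolment, codes reach the site, the 20 patients are enrolled over 26 to 52 weeks, and data entry takes 0 to 4 weeks.

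*Lag* is the number of most recent patients not yet unblinded when the next is treated. Spacing is 26/20 = 1.3 to 52/20 = 2.6 weeks. Delay is 4/7 = 0.57 to 11/7 + 4 = 5.57 weeks. Lag = ceil(delay/spacing) − 1, so the smallest is ceil(0.57/1.3) − 1 = 0 and the largest is ceil(5.57/1.3) − 1 = 4.

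*Certain allocations, unblocked.* At lag 0 a patient is certainly active once all four placebo codes are known: expected 16/(4+1) = 3.200. A patient is certainly placebo once all 16 active codes are known: 4/(16+1) = 0.235. Moving from lag k−1 to lag k subtracts the probability that the last k allocations are all of that kind:

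- Active, lag 1: 3.200 − 16/20 = 2.400.
- Active, lag 2: 2.400 − (16×15)/(20×19) = 1.768.
- Placebo, lag 1: 0.235 − 4/20 = 0.035.
- Placebo, lag 2: 0.035 − (4×3)/(20×19) = 0.004.

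*Best guess.* With no codes known, guessing active throughout is right for 20 × 0.8 = 16.0 patients. With codes known, each patient is guessed as the likelier treatment, averaged over all C(20,4) = 4845 lists.

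*Blocks of five, one placebo each.* Per block at lag 0: 4/2 + 1/5 = 2.2, and 4 × 2.2 = 8.8 overall.

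| Lag | Certain, unblocked (active + placebo) | Best guess correct, unblocked | Certain, known blocks of 5 |
|---|---|---|---|
| 0 | 3.44 (3.20 + 0.24) | 16.28 | 8.8 |
| 1 | 2.44 (2.40 + 0.04) | 16.08 | 4.8 |
| 2 | 1.77 | 16.05 | 2.4 |
| 3 | 1.28 | 16.02 | 0.8 |
| 4 | 0.90 | 16.01 | 0 |

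With known blocks of five the best guess is 16.8 at lag 0 and 16.0 at every longer lag. For the unblocked list, the chance that any placebo patient becomes certain is 4/20 = 20% at lag 0, (4×3)/(20×19) = 3.2% at lag 1 and 0.4% at lag 2. What can be learnt is almost entirely that a patient is on active treatment, which 4:1 allocation already makes the likely guess.

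**The case against.** The strongest reply is that this is a rule with a stated exception, which is ordinary drafting. Section 3.5.3 puts both in one paragraph, and section 5.5.2 is the place for exceptions to 5.5.1. Sections 3.5.1 and 5.5.1 do not mention emergency or expedited unblinding either. The looser wording may reflect timing: expedited unblinding can occur before a patient's data are complete, whereas this clause applies only afterwards. This stands. A reader might infer that the protocol contradicts its own double-blind design, or that section 9.3 is breached. The documents do not support either: section 5.5.1 is already qualified by role, and unblinding of the data in 9.3 can mean the code break for the whole dataset.

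The routes to bias are also limited. Major deviation criteria are to be set in the statistical analysis plan, and the other per-protocol criterion is numeric (baseline HVPG of at least 12 mmHg). Section 9.6 uses the full analysis set as well as the per-protocol set. Duplicate readings and permanent tracings constrain the operator. Blood pressure and pulse may hint at treatment anyway: section 3.5.4 reports a maximum mean rise of 14 mmHg in mean arterial pressure in healthy subjects at the highest planned infusion rate. The placebo comparison is acknowledged to have limited power (section 9.6.1). All this keeps the harm small.

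Finally, removing the clause outright could have a cost. Section 4.5 sends the matter to the Safety Review Committee when criteria are met in at least two subjects on the same treatment. In Part 2 that requires treatment knowledge, which the emergency and expedited routes do not clearly cover. The documents do not say that the clause serves this purpose, but the fix has to allow for it.

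What the reply does not answer is that the exception has no decision-maker, no recipients and no link to the end of Part 2. Documenting a broken blind makes its use traceable but does not prevent it.

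**Conclusion.** The point holds as a cheap improvement to the plan. The clause opens an avoidable gap between data entry and the decisions that should be made blind, at a single site where the same people continue to measure and assess.

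A reader might go further and infer that the blind fails or that later allocations become largely predictable. The documents do not support that. The clause is discretionary, nothing says codes would go to the site, and even with that assumption, exact 16:4 and zero lag, an unblocked list yields at most 0.28 extra correct guesses in 20. The larger count of 8.8 certain allocations needs known blocks of five as well, and there the gain is 0.8 correct guesses at zero lag and none at longer lags.

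Route 1 needs only that the clause be used before the review and that those rating deviations learn the treatment. Its effect cannot be sized from the documents.

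**What to change.** In sections 3.5.3 and 5.5.2, limit the sentence so that it applies only after deviation review, per-protocol decisions and database lock for all of Part 2. Refer to it in sections 3.5.1 and 5.5.1 so that the four places agree.

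Keep:

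- emergency and expedited-reporting unblinding as in section 5.5.2;
- the monitor, pharmacist and bioanalysis roles in section 5.5.1;
- restricted treatment access for the Safety Review Committee where section 4.5 requires knowing that subjects received the same treatment. State who holds the codes, and keep the measuring and assessing site staff blinded as far as possible. Section 3.4 makes the Principal Investigator a committee member, so this needs to be spelled out.

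The cost is a sentence edited in two places, short cross-references, and a line on committee access. The sponsor and site lose the option of an early look at individual treatments, a need for which the documents give no reason.
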